2.2.1 Subgroup of interest

The subgroups of interest for this study are:

- GCA diagnosis
 - New onset GCA (defined as GCA diagnosis date within 6 weeks of Baseline visit date or there is a protocol deviation, in relation to inclusion criteria 5, regardless of protocol deviation discrepancy status)
 - Relapsing disease GCA (defined as GCA diagnosis date > 6 weeks from Baseline visit
- Baseline co-administered prednisolone treatment
 - $\geq 40 \text{ mg/day}$
 - < 40 mg/day

2.3 Patient disposition, demographics and other baseline characteristics

Patient disposition, background and demographic characteristics will be reported for the RAS, unless otherwise specified.

No inferential tests for differences in background and demographic characteristics will be performed.

2.3.1 Patient disposition

Patient disposition will be summarized using:

- Study treatment disposition
- Study disposition

Note: Patients may stop study treatment but continue to stay in the study hence there will be a differentiation between study treatment and study disposition. Patients will be analyzed according to the treatment assigned at the last randomization (see Section 2.2 for further details).

The number and percentage of patients who completed study treatment, those who discontinued study treatment prematurely, along with the primary reason for study treatment discontinuation, will be presented for each treatment group and overall (i.e. all patients) for the RAS.

A similar summary table will be presented for study disposition, i.e. the treatment disposition phase.

All patient disposition data will be listed by treatment group, center, and subject number for the RAS.

In additition, for the legal requirements of clinicaltrials.gov and EudraCT, the number and percentage of patients enrolled in each site will be provided.

2.3.2 Demographics and other baseline characteristics

Demographics and other baseline characteristics data will be summarized for each treatment group and overall (i.e. all patients) for the FAS. Patients will be analyzed according to the treatment assigned at the last randomization (see Section 2.2 for further details).

Descriptive statistics will be presented for the following continuous demographic and other baseline characteristics variables:

- Age (years)
- Height (cm)
 - Note: This will be presented for each treatment group and overall and in addition for each sex category in each treatment group and overall.
- Weight (kg)
 - Note: This will be presented for each treatment group and overall and in addition for each sex category in each treatment group and overall.
- Body mass index (BMI) (kg/m²)
 - Defined as: (body weight in kg) / (height in meters)²

For BMI, height and body weight used is the last value prior to first administration of study treatment. If there is no weight recorded prior to taking the study treatment, BMI will be missing.

Note: This will be presented for each treatment group and overall and in addition for each sex category in each treatment group and overall.

- Time since diagnosis of GCA (years)
 - Defined as: (date of Visit 1 date of diagnosis of GCA) / 365.25 For handling of missing or incomplete GCA diagnosis dates, refer to Section 5.1.4.
- Time since first GCA symptom (years)
 - Defined as: (date of Visit 1 date of first GCA symptom) / 365.25
 For handling of missing or incomplete first GCA symptom dates, refer to Section 5.1.4.
- GCA diagnosis (New onset GCA, Relapsing disease GCA)
- Baseline co-administered prednisolone treatment (≥ 40 , < 40 mg/day)

The number and percentage of patients in each category of the following categorical variables overall will be presented:

- Weight group $(< 70, \ge 70 \text{ to } < 90, \ge 90 \text{ kg})$
- Current smoking status (Current, Former, Never)
- Race (White, Black or African American, Asian)
- Sex (Male, Female)

All important demographics and other baseline characteristics data will be listed by treatment group, center, and subject number for the RAS.

In addition, for the legal requirements of clinicaltrials.gov and EudraCT, the following age categories will also be presented:

- 18 to < 65 years
 - Note: Inclusion criteria 3 indicates that patients must be at least 50 years of age to be included in this study. Therefore for this study the subgroup category 18 to < 65 years is equivalent to 50 to < 65 years.
- 65 to < 85 years
- ≥ 85 years

2.3.2.1 Medical history

Relevant medical histories and current medical conditions at the time of informed consent will be summarized for each treatment group and overall (i.e. all patients) for the FAS.

Note: If there are COVID-19 infected patients in this study, descriptive summaries of medical history will be provided first by all patients of interest, then by COVID-19 infected patients and non-COVID-19 infected patients.

The summaries will be presented by primary system organ class (SOC) and preferred term (PT). Medical histories will be coded using the most recent (i.e. latest version as per clinical database lock [CDBL]) Medical Dictionary for Regulatory Activities (MedDRA). The primary SOCs

will be presented in alphabetical order and the PTs will be presented by decreasing proportion in the overall group.

2.3.2.2 Cardiovascular medical history

Cardiovascular medical history will be presented by treatment group and overall (i.e. all patients) for the Safety Set.

Note: If there are COVID-19 infected patients in this study, descriptive summaries of medical history will be provided first by all patients of interest, then by COVID-19 infected patients and non-COVID-19 infected patients.

The number and percentage of patients with an occurrence of the following events will be provided:

- Type 1 diabetes
- Type 2 diabetes
- Hypertension
- Dyslipidemia/Hyperlipidemia
- Prior transient ischemic attack
- Prior hemorrhagic stroke
- Prior ischemic stroke
- Prior stroke: unknown type
- Myocardial infarction
- Atrial fibrillation
- Supraventricular tachycardia
- Deep vein thrombosis
- Pulmonary embolism
- Peripheral arterial disease
- Stable coronary artery disease
- Gout

In addition, the number and percentage of patients with an ongoing event at Baseline will be provided in a summary table by treatment group and overall (i.e. all patients) for the Safety Set.

2.3.2.3 GCA medical history

GCA medical history will be presented by treatment group and overall (i.e. all patients) for the Safety Set.

Note: If there are COVID-19 infected patients in this study, descriptive summaries of medical history will be provided first by all patients of interest, then by COVID-19 infected patients and non-COVID-19 infected patients.

The number and percentage of patients with an occurrence of the following events will be provided:

• Diplopia

- Blurring of vision
- Transient partial visual loss (Amaurosis fugax) Left eye
- Transient partial visual loss (Amaurosis fugax) Right eye
- Visual field defect Left eye
- Visual field defect Right eye
- Loss of vision Left Eye
- Loss of vision Right Eye
- Relative afferent pupillary defect
- Headache
- Scalp tenderness
- Claudication of jaw muscles
- Temporal artery abnormality
- Fever
- Night sweat
- Weight loss
- Large vessel involvement
- Polymyalgia rheumatica

In addition, the number and percentage of patients with an ongoing event at Baseline will be provided in a summary table by treatment group and overall (i.e. all patients) for the Safety Set. Only the following GCA medical history events can be classified as ongoing or not at Baseline:

- Diplopia
- Blurring of vision
- Transient partial visual loss (Amaurosis fugax) Left eye
- Transient partial visual loss (Amaurosis fugax) Right eye
- Relative afferent pupillary defect

2.3.3 Protocol deviations

The number and percentages of patients with each important protocol deviation type will be tabulated by treatment group and overall (i.e. all patients) for the FAS. The results will be grouped using the broad categories defined in the current Standard Operating Procedure (SOP) which are:

- Patient did not satisfy entry criteria
- Patient received the wrong treatment or incorrect dose
- Patient developed study/treatment withdrawal criteria during the study, but was not withdrawn
- Patient took an excluded concomitant medication
- Others

All important protocol deviations will be listed by treatment group, center, and subject number for the FAS.

Note: There is no per protocol analysis set in this study. Therefore no protocol deviation will lead to exclusion from any of the analysis sets.

In addition, pandemic related protocol deviations will be summarized by category and relationship. All COVID-19 related protocol deviations will also be listed for the FAS.

2.4 Treatments (study treatment, rescue medication, concomitant therapies, compliance)

Summaries will be presented for the Safety Set. Patients will be analyzed according to treatment received (see Section 2.2 for further details).

2.4.1 Study treatment / compliance

The number and percentage of study treatment injections will be summarized by treatment group by means of contingency tables.

In case it cannot be identified from the data collected or assumed from the planned treatment whether an injection contained placebo or secukinumab, it will be assumed that the syringe contained secukinumab.

The duration of exposure to study treatment will be summarized by treatment group. Duration of exposure to study treatment will be defined as the time from first dose of study treatment to the end of the treatment period. The end of treatment period will be defined as the last dose of the study treatment plus 84 days or last visit whichever occurs earlier. i.e., for patients who discontinued or have their last visit earlier than last dose of study treatment plus 84 days, the end of study treatment exposure will be the date of the last study visit in the corresponding treatment period.

Duration of exposure (weeks) = (min(end of treatment period date, last dose of study treatment date + 84 days) - first dose of study treatment date + 1)/7

The number of patients with exposure of the following time thresholds will be displayed:

- any exposure
- ≥ 1 week
- ≥ 2 weeks
- \bullet > 3 weeks
- \geq 4 weeks
- ≥ 8 weeks
- ≥ 12 weeks
- ≥ 16 weeks
- ≥ 20 weeks
- \geq 24 weeks
- ≥ 28 weeks
- \geq 32 weeks
- ≥ 36 weeks> 40 weeks

- > 44 weeks
- > 48 weeks

Descriptive statistics will also be provided for the study treatment group for the following:

- Actual cumulative dose
 - Defined as: the sum of all doses of study treatment during the treatment disposition phase
- Dose intensity

Defined as: the ratio of actual cumulative dose of study treatment received and actual duration of exposure of study treatment (weeks)

Note: Each study treatment injection is equivalent to 150 mg. Patients assigned to study treatment should take 2 injections (150 mg) weekly from Week 0 to Week 4 and then every 4 weeks until Week 48.

The duration of exposure to the co-administered prednisolone treatment will also be summarized by treatment group using the same logic and rules as the study treatment (with the exception that the addition of 84 days is only applicable to study treatment). In addition descriptive statistics of the average daily dose (mg/day) of co-administered prednisolone treatment overall during the study and at each week (refer to Table 2-2 for weekly visit windowing) during the 26-week prednisolone taper regimen will be presented for each treatment group.

Furthermore descriptive statistics of the co-administered prednisolone treatment at the time of first flare post-baseline will also be provided.

Co-administered prednisolone treatment data will be listed by treatment group, center, and subject number for the Safety Set. In addition, a co-administered prednisolone treatment data listing will also be provided for the subset of patients who did not adhere to the prednisolone taper regimen.

2.4.2 Prior, concomitant and post therapies

Medications will be identified by Anatomical Therapeutic Chemical (ATC) class and PT according to the World Health Organization (WHO) Drug Reference List dictionary (version 18.9 or a more recent version).

Note: If there are COVID-19 infected patients in this study, descriptive summaries of prior and concomitant medications will be provided first by all patients of interest, then by COVID-19 infected patients and non-COVID-19 infected patients.

Summaries will be presented separately for prior and concomitant medications. Tables will show the number and percentage of patients receiving at least one dose of the therapy.

Note: Methotrexate (MTX) will not be included in the aforementioned summaries for prior and concomitant medications. Separate summaries will be created for prior and concomitant use of MTX.

Prior medications are defined as drugs taken and stopped prior to first dose of study treatment. Any medication given at least once between the day of first dose of randomized study treatment and the last day of study visit will be a concomitant medication, including those which were started pre-baseline and continued into the treatment period.

Prior or concomitant medication will be identified based on recorded or imputed start dates of medication taken in this study. The rules for imputing incomplete start dates are described in Section 5.1.3. All prior and concomitant medication data will be listed by treatment group, center, and subject number.

In addition, medical procedures and significant non-drug therapies as coded in MedDRA will be summarized.

2.4.3 Signs and symptoms of GCA

The number and percentage of patients who experienced flare due to GCA will be summarized by visit for each treatment group and overall (i.e. all patients). The summary table will also include the number and percentage of patients with each of the following individual signs and symptoms of GCA:

- Fever (Yes, No)
- Symptoms of polymyalgia rheumatica (PMR) (Yes, No)
- Localized headache, temporal artery or scalp tenderness (Yes, No)
- Acute or subacute vision loss due to arteritic anterior ischemic optic neuropathy(A-AION)
 (Yes, No)
- Transient blurry vision (generally monocular or at least affecting one eye at a time, but potentially affecting both eyes) (Yes, No)
- Jaw or mouth pain (Yes, No)
- New or worsened extremity claudication (Yes, No)
- Other features judged by both the clinician-investigator to be consistent with a GCA or PMR flare (Yes, No)

Note: More than 1 sign and symptom of GCA may be selected.

2.5 Analysis of the primary objective

Patients will be analyzed according to the treatment assigned at the last randomization (see Section 2.2 for further details).

2.5.1 Primary endpoint

The primary endpoint is the proportion of GCA patients who are in sustained remission until Week 28.

The analysis of the primary variable will be based on the following estimand:

- Analysis set: FAS (for the patients of interest as outlined in Section 2.1)
- Variable of interest: Proportion of GCA patients who are in sustained remission until Week 28
 - Sustained remission: Patients without flare until Week 28 and in adherence to the protocol prednisolone taper regimen.

- Note: Flare is determined by the investigator and defined as the recurrence after remission of signs or symptoms of GCA and/or ESR \geq 30 mm/hr and/or CRP \geq 10 mg/L attributable to GCA.
- Adhere to prednisolone taper: Patients do not adhere to the prednisolone taper regimen if during the 26-week prednisolone taper regimen any of the following occur:
 - Patient does not take prednisolone medication for GCA for ≥ 6 consecutive days.
 - Patient takes prednisolone treatment for GCA for < 80% of the 26-week prednisolone taper regimen period.
 - Patient has received additional prednisolone for GCA to that stated in the taper regimen.

Note: This criteria (receiving additional prednisolone) does not apply to those patients in the "escape arm".

This means a patient is classified as receiving an additional prednisolone for GCA to that stated in the taper regimen if in the timeframe:

- [Week 0-Week 11] the patient's weekly dose is 20% over the stated dosage of prednisolone, or
- [Week 12-Week 26] the patient's weekly dose is 30% over the stated dosage of prednisolone.
- Patient received an additional corticosteroid to that stated in the taper regimen. Note: This will be based on the respective PD associated with this criteria.

Note: The final decision on whether the patient is non-adherent to the prednisolone taper will be confirmed by the blinded medical team on a by-patient basis in a Blind Data Review Meeting (BDRM) prior to CDBL. This decision will be documented in the associated BDRM minutes.

- Intervention effect: Effect between secukinumab versus placebo at Week 28 regardless of adherence to randomized treatment.
- Measure of intervention effect: Odds ratio (OR).

2.5.2 Statistical hypothesis, model, and method of analysis

The primary endpoint variable of interest is binary, hence a binomial distribution will be assumed for the observed data from this study. It is of interest to estimate a one-dimensional scalar parameter (the primary endpoint estimand Θ) using Bayesian inference.

To perform this inference, a prior distribution for Θ must first be specified. The response rate of the comparable placebo arm of the GIACTA study (Stone et al 2017) will be used as the prior distribution for the placebo response rate for the primary endpoint in this study. The parameters of this Beta distribution are 10 and 43, i.e. Beta (10, 43). The prior distribution for the response rate on secukinumab will be a Beta distribution with parameters 0.5 and 0.5, i.e. Beta (0.5, 0.5). This prior distribution was chosen because it has low weight to reflect the lack of current knowledge on the response rate on secukinumab in GCA.

The process of Bayesian inference involves passing from a prior distribution, $p(\Theta)$, to a posterior distribution, $p(\Theta|y)$ where y refers to the data of interest from this study. Due to the conjugate nature of the Beta distributions, the posterior distributions of the primary endpoint

estimand Θ will also be Beta distributions. As the Beta distribution has a closed form nature, descriptive statistics of the posterior distribution are also available in closed form.

Using the prior distribution information and the study data, the Beta posterior distribution for each treatment group will be derived.

$$\Theta|y \sim Beta(y + a, n - y + b)$$

Note: y = study data (i.e. proportion of GCA patients who are in sustained remission until Week 28) for the treatment of interest; n = number of randomized patients for the treatment of interest; a, b = the shape parameters from the prior Beta distribution [Beta(a,b)] associated with the treatment of interest.

One hundred thousand random draws from the Beta posterior distributions will then be taken based on the seed 190207. An estimate of the 95% posterior interval (i.e. the 95% credibility interval), using the the 2.5 and 97.5 percentiles as well as the median (50 percentile) will be obtained. The median and 95% credibility interval of the OR, risk difference (RD) and risk ratio (RR) will be presented.

Note: Odds ratio is the ratio of odds of the primary endpoint in secukinumab to the odds of the event in placebo. The odds of an event refers to the number of events / the number of non-events. Risk difference is the difference in proportions of the patients with the primary endpoint in secukinumab vs placebo. Risk ratio (also known as relative risk) is the ratio of risk of the primary endpoint in secukinumab to the risk of the primary endpoint in placebo.

For this study, similar response rates to the GIACTA study (Stone et al 2017) for the primary endpoint are expected, i.e. 56% secukinumab response rate and 18% placebo response rate. If the secukinumab response rate was < 40% this may indicate that further trials in this indication would not be worthwhile. Therefore assuming the 18% placebo response rate is fixed, the treatment response rates would translate into a RD of:

- 38% (expected effect, based on 56%-18%)
- 22% (minimal effect, based on 40%-18%)

This study would suggest to proceed with the development of secukinumab in this indication, if the following GO-criterium are satisfied:

• the posterior probability of a relevant effect (RD > 0.22) is at least 50% (also written as $prob(RD > 0.22 \mid y) \ge 50\%$)

and

• the posterior probability of any effect (RD > 0) is at least 90% (also written as prob(RD > 0 $|y| \ge 90\%$)

The posterior probabilities for a relevant effect and for any effect will be determined to give guidance in deciding whether to proceed in the development of secukinumab in this indication.

The posterior probability of the OR and the RR of the comparison of secukinumab versus placebo being greater than 1 will also be provided. Note: An OR or RR greater than 1 indicates a favourable outcome for secukinumab vs placebo in regard to the primary endpoint.

Furthermore, the proportion of patients in sustained remission until Week 28 (Yes, No) will be summarized descriptively by treatment group. This analysis does not take into account the prior information, it is only based on information from this study.

In addition, all primary endpoint data will be listed by treatment group, center, and subject number for the FAS.

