- The Randomized Analysis Set (RAS) consists of all randomized patients. Unless otherwise specified, mis-randomized patients will be excluded from the RAS. (Misrandomized patients are defined as cases where patients were mistakenly randomized by the investigator/qualified site staff either prematurely or inappropriately prior to confirmation of the patient's final randomization eligibility and double-blind treatment was not administered to the patient. If patients were re-screened and successfully randomized they will be included in the RAS according to the treatment assigned in the last randomization.)
- The Full Analysis Set (FAS) comprises all patients to whom study treatment has been assigned by randomization and who received at least one dose of randomized study treatment (secukinumab or placebo). According to the intent to treat principle, patients will be analyzed according to the treatment assigned to them at randomization.
- The Safety Set includes all patients who received at least one dose of study treatment (secukinumab or placebo). Patients will be analyzed according to the study treatment received, where treatment received is defined as the treatment the patient received on the first day of study treatment.

The number of patients within each of the analysis sets used in this study will be summarized by treatment group and overall (i.e. all patients).

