5.5 Statistical models

Primary analysis

SAS Code for Bayesian Analysis

The Bayesian analysis will be performed using SAS.

Note that for this illustrative example:

- the data are stored in the file data_set
- response1 = number of patients in the secukinumab treatment group who fulfil the primary endpoint

- number1 = number of patients in the secukinumab treatment group in the population of interest
- a1, b1 = the shape parameters from the prior Beta distribution [Beta(a,b)] associated with the secukinumab treatment group
- response2 = number of patients in the placebo treatment group who fulfil the primary endpoint
- number 2 = number of patients in the placebo treatment group in the population of interest
- a2, b2 = the shape parameters from the prior Beta distribution [Beta(a,b)] associated with the placebo treatment group

```
data <data set>;
*** set the seed;
call streaminit(190207);
  *** one hundred thousand draws from the Beta posterior distributions;
  do draw=1 to 100000;
    ***secukinumb treatment group;
   post resp1=RAND('BETA', <a1>+<response1>, <number1>+<b1><response1>);
    ***placebo treatment group;
   post resp2=RAND('BETA', <a2>+<response2>, <number2>+<b2>-<response2>);
    ***risk difference;
   rd=post resp1 - post resp2;
    ***risk ratio;
   rr=post resp1/post resp2;
    ***odds ratio;
    or=(post resp1/(1 - post resp1))/(post resp2/(1 - post resp2));
  end;
run;
***obtain percentiles of interest to determine median and 95%
credibility interval;
proc univariate data=<data set>;
  var post resp1 post resp2 rd rr or;
  output out=percentiles1 pctlpts=2.5 25 50 75 97.5 pctlpre=post1
post2 rd rr_ or_;
run;
***determine probabilities of interest;
proc sql;
 create table prob1 as
  select mean(or gt 1) as probnor1,
         mean(rd gt 0.22) as probnrd1,
         mean(rd gt 0.38) as probnrd2,
         mean(rd gt 0) as probnrd3,
         mean(rr gt 1) as probnrr1
  from <data set>;
quit;
```

Secondary analysis

SAS Code for Kaplan-Meier Plot

Novartis
SAP Amendment 1

The time to event analysis will be performed using the SAS procedure PROC LIFETEST.

Note that for this illustrative example:

- the data are stored in the file data set
- timevar = survival time
- censorvar = censoring variable (Note: 1 indicates a censored time)
- stratavar = stratification variable

```
ODS GRAPHICS ON;

PROC LIFETEST DATA=<data_set> PLOTS=survival (failure test at risk(outside(0.15))=0 to 360 by 30);

TIME <timevar> * <censorvar> (1);

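### SAP 2.5.2 defines n in the primary posterior as randomized patients although the analysis set is the FAS, and calls y a proportion; the effect is small, but the definitions need correcting

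*SAP*

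**What the plan says.** SAP 2.5.1 sets the population for the primary estimand: "Analysis set: FAS (for the patients of interest as outlined in Section 2.1"). Protocol 9.4.1 names the same set. SAP 2.2 limits the FAS to randomized patients "who received at least one dose of randomized study treatment (secukinumab or placebo"), and Table 5-5 in SAP 5.6 separates the RAS from the FAS by the absence of any study drug.

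SAP 2.5.2 then gives the posterior for each arm as Beta(y + a, n - y + b) and defines its two data inputs. The responder term is given as "y = study data (i.e. proportion of GCA patients who are in sustained remission until Week 28) for the treatment of interest". The denominator, on which the conflict with the analysis set turns, is given as "n = number of randomized patients for the treatment of interest".

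The program in SAP 5.5 takes a count as numerator, "response1 = number of patients in the secukinumab treatment group who fulfil the primary endpoint", and a generic denominator, "number1 = number of patients in the secukinumab treatment group in the population of interest".

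SAP section 4, which lists departures from the protocol's analyses, mentions no move from the FAS to randomized patients.

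**The concern.** The formula that produces the primary result should have a single reading, and here its denominator names a population other than the stated analysis set. A patient who is randomized but never dosed adds one to n and nothing to y, so lands in n - y as a non-responder, while the FAS excludes that patient altogether.

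The documents do foresee such patients. SAP 2.1.1.6 gives them a baseline date, and protocol 6.1.1 says how to record patients who are randomized but do not start treatment.

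The denominator feeds a numeric rule. SAP 2.5.2 suggests proceeding with development if P(RD > 0.22) is at least 50% and P(RD > 0) is at least 90%. With about 25 patients per arm, one patient can shift the first probability by several points near its threshold. A wrong n would also be hard to notice, because 26 in place of 25 still gives a plausible answer.

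**Working it through.** **Inputs.** Priors for the analysis: secukinumab Beta(0.5, 0.5), placebo Beta(10, 43) (SAP 2.5.2). GO rule as above (SAP 2.5.2). Arm size 25 and expected responders 14 and 4 (SAP 3). Assumption: an undosed patient, if counted in n, is a non-responder, as the missing-information rule in SAP 2.5.3 would imply. Probabilities were obtained by numerical integration of the two Beta densities.

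**The plan's own figure first.** Table 3-1, row 1, uses 14/25 and 4/25 with Beta(1, 1) for secukinumab. With y as a count the posteriors are Beta(15, 12) and Beta(14, 64). The 2.5%, 50% and 97.5% points of the difference come to 0.170, 0.378 and 0.573, against the printed 0.19, 0.38 and 0.56. The median agrees. The limits are off by up to 0.02, which is more than the spread over 200 repeats of 10,000 draws (0.161 to 0.177 and 0.567 to 0.581). Over all six rows the medians agree within 0.01 and the limits within 0.02. The table is thus broadly reproduced with counts.

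**Effect of n: one undosed secukinumab patient in addition to 25 dosed.** The posterior changes from Beta(0.5 + y, 0.5 + 25 - y) to Beta(0.5 + y, 0.5 + 26 - y). With 4/25 on placebo, the placebo posterior is Beta(14, 64), mean 14/78 = 0.179.

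| Responders (secukinumab vs placebo) | Secukinumab posterior mean, n = 25 | n = 26 | P(RD > 0.22), n = 25 | n = 26 |
|---|---|---|---|---|
| 14 vs 4 (planned) | 14.5/26 = 0.558 | 14.5/27 = 0.537 | 0.931 | 0.905 |
| 10 vs 4 (boundary) | 10.5/26 = 0.404 | 10.5/27 = 0.389 | 0.510 | 0.452 |

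In the second row the difference in posterior means goes from 0.404 - 0.179 = 0.225 to 0.389 - 0.179 = 0.210, so it crosses 0.22. That is why the result turns.

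**Same question with 25 randomized and 24 dosed on secukinumab.** With 10 responders versus 5/25 on placebo, P(RD > 0.22) is 0.523 with n = 24 (FAS) and 0.462 with n = 25.

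**How often this would matter.** For 0 to 15 placebo responders, every result where the choice of n changes the GO decision was listed and weighted by its binomial probability, with a true placebo rate of 18%. The figures are conditional on one undosed secukinumab patient:

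| True secukinumab rate | 25 dosed + 1 undosed | 24 dosed of 25 |
|---|---|---|
| 40% | 7.4% | 5.3% |
| 50% | 5.5% | 3.6% |
| 56% | 3.0% | 1.9% |

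An undosed placebo patient changes no decision in the 25 + 1 case. In the 24-of-25 case it changes one result only, 9/25 versus 1 responder, with 0.500 (just below the threshold) against 0.507. P(RD > 0) stays above 0.96 in every changed case, so the second criterion never decides.

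**Effect of y read literally.** Putting 0.56 and 0.16 into the formula with n = 25 gives posterior means (0.5 + 0.56)/26 = 0.041 and (10 + 0.16)/78 = 0.130, and P(RD > 0) = 0.055. With counts P(RD > 0) is 0.9999. The literal reading cannot be what was meant.

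**The case against.** The best defence is that the SAP already shows what is intended. SAP 2.5.1 names the FAS, SAP 2.5.2 lists the primary endpoint data for the FAS, the binomial model and the program require counts, and section 3 plans in counts. That holds for y: the word proportion is a slip that the program overrides, and nobody following the SAP would enter 0.56. A reader might infer from the literal arithmetic that the secukinumab posterior is meaningless; the documents do not support that.

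A reader might also infer that the program contradicts the FAS on n. It does not. Its denominator is the population of interest, which defers to the analysis set chosen elsewhere. The conflict on n is between the note in SAP 2.5.2 and the analysis set in SAP 2.5.1 and protocol 9.4.1. Equally, the program does not name the FAS, so it does not resolve that conflict.

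The third tempting inference is that any one untreated patient would overturn the GO decision. That needs a boundary result and, in practice, a patient in the secukinumab arm. Such patients should be rare: randomization and the first on-site injection both belong to the Baseline visit, and SAP 2.2 says "Unless otherwise specified, mis-randomized patients will be excluded from the RAS", which covers those randomized in error and not dosed. This limit stands, although SAP 2.5.2 speaks of randomized patients and not of the RAS, so the exclusion is not expressly carried over. The SAP also describes the posterior probabilities as guidance, and the summary measure of the estimand is the odds ratio.

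Finally, SAP 2.5.3 would classify an undosed patient as a non-responder if that patient were in the analysis. That explains how the patient would be counted; it does not justify counting someone the FAS excludes.

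**Conclusion.** The point holds as a correction to one note. The definition of n in SAP 2.5.2 is wrong as written, because it contradicts the analysis set in SAP 2.5.1 and protocol 9.4.1 and no change is declared in SAP section 4. The definition of y is a wording error without analytic effect.

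The consequence is modest: a shift of 0.026 in P(RD > 0.22) at the planned response (0.931 - 0.905), and of 0.058 at the boundary example (0.510 - 0.452). Given one undosed secukinumab patient, the chance that the GO decision depends on the choice of n is about 2% to 7% over true secukinumab rates of 40% to 56%. The unconditional chance is lower, but the documents give no expected number of such patients from which to compute it. These figures assume arms of about 25, a true placebo rate of 18% and non-response for the undosed patient. Since the primary formula should leave no choice of denominator to be made at the time of analysis, the text should be corrected.

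**What to change.** In SAP 2.5.2 define y as the number of FAS patients in the arm who are in sustained remission until Week 28, and n as the number of FAS patients in the arm. In SAP 5.5 keep the generic inputs, since the same code can serve the subgroup analyses, and add one sentence: for the primary analysis the population of interest is the FAS, and for a subgroup analysis it is the FAS patients in that subgroup. The cost is two definitions and one sentence, with no new data and no change to the program.
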